Cost Measurement. Costs to be collected can be grouped into three broad categories: intervention delivery costs, participant time costs, and health care costs. Intervention costs incurred to develop both interventions will be excluded from the analysis as these costs have already been incurred and are thus “sunk” costs. Intervention Delivery Costs for both conditions will be estimated using both standardized estimates and convenience sampling of support staff and our interventionists. The time it takes to prepare for and execute CBT for SUD is specified in the treatment manual but will be assessed through a data tracking system, surveys, and counselor records to validate these estimates. Similar methods will be used to estimate time spent in identifying veterans with AUD, contacting veterans, and training veterans on the use of the mCM smart phone app. To reduce burden, we will not measure every activity for every subject for every occasion. Instead we will collect a convenience sample of observations toward the beginning and the end of the study to account for the fact that there may be a learning curve effect. The size of the convenience sample will depend on the variability we observe in the activity times—the larger the variability the larger the sample we will collect. In addition to labor costs, materials costs, including the cost of the mCM will be included.

Participant Time Costs (i.e., the opportunity costs to participants). This will include the time spent by participants in using the intervention strategies, techniques, or information. As part of the end-of-treatment follow-up, time spent on the intervention materials other than that involved in the treatment sessions will be assessed. In the intervention arm, the number of videos submitted will be used to assess the time involved in providing bioverification as part of mCM. We will derive participant time cost estimates for each group by combining the time estimates with standard wage estimates adjusted for age, gender, and if possible race, derived from the Statistical Abstract of the United States. Because we chose to conduct the cost-effectiveness analysis from the societal perspective, the use of mean wage rates has higher generalizability and validity than self-reported wages by the subjects. *Health care costs* will be obtained from VA medical records for outpatient, inpatient and medication use one year prior to trial enrollment and through the final follow-up.

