D.8.7. Treatment Fidelity. Counselors will receive weekly supervision for CBT from [name] or another senior clinician. Following procedures recommended by the VA training program, we will utilize the Cognitive Behavioral Therapy for Substance Use Disorders Rating Scale to measure counselor adherence in delivering behavioral treatments for substance abuse disorders (Gnys, DeMarce, Raffa, & Karlin, 2014). A random selection of 10% of the counseling sessions will be rated for fidelity by rater who is otherwise independent of the conduct of the study. Fidelity ratings will be used in supervision to improve counseling. To measure therapeutic alliance, we will use the 16-item Individual Treatment Alliance Scale Revised Short Form, which has a demonstrated relationship with treatment dropout and treatment response in behavioral interventions (Pinsoff, Zinbarg, & Knobloch-Fedders, 2008). This measure will be given at the final treatment session for all participants, including participants who withdraw early from treatment.

D.8.8. Outcome Measurement and Biochemical Verification. At each treatment session, and at post-treatment and follow-ups, we will measure number of heavy drinking days (> 5 drinks in day for men, > 4 drinks in a day for women), binge drinking episodes (heavy drinking within a 2-hour period), number of drinking days, and drinks per drinking day. At follow-ups, we will conduct Timeline Follow-back interviews to improve self-reports of drinking behavior over the previous months. We will ask participants to complete items from the Addiction Severity Index (ASI) to assess the consequences of substance use on functioning in the previous month. Participants will complete all of the items of the Employment subscale, and items 1, 3, 7, 8, 9, 10, 28, 29, 30, 31, 32, and 34 of the Family/Social subscale. Early continuous abstinence will be defined as three consecutive weeks of alcohol abstinence in the first eight weeks after the quit attempt, a threshold that has been predictive of good long-term SUD outcomes (Carroll et al., 2014). We will bioverify self-reports of low risk drinking with fingerstick blood spot samples for PEth testing at 6-month and 12-month follow-ups.

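### The sampled staff times are a convenience sample from the two ends of the study, so mCM unit costs are open to bias of either sign that the planned sensitivity analyses would not show

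*Combined protocol and SAP*

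**What the plan says.** The cost measurement text in D.6 names several sources for delivery cost: "Intervention Delivery Costs for both conditions will be estimated using both standardized estimates and convenience sampling of support staff and our interventionists". For CBT, "The time it takes to prepare for and execute CBT for SUD is specified in the treatment manual", and the time "will be assessed through a data tracking system, surveys, and counselor records to validate these estimates". Other staff work follows the same route: "Similar methods will be used to estimate time spent in identifying veterans with AUD, contacting veterans, and training veterans on the use of the mCM" app.

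Measurement is deliberately partial: "To reduce burden, we will not measure every activity for every subject for every occasion". The rule for what is measured is: "Instead we will collect a convenience sample of observations toward the beginning and the end of the study", and the reason given for two windows is "to account for the fact that there may be a learning curve effect". The sample grows with the variability seen in the activity times.

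D.6 does not say how observations are picked, how long the windows are, how they are weighted, or how sampled times are combined with the standardized estimates. Under Aim 2, Section F plans a nonparametric bootstrap of the ICER and sensitivity analyses on abstinence, relapse, mortality and long-term alcohol costs. Staff time is not in that list.

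D.8.7 already provides a probability sample of sessions for another purpose: "A random selection of 10% of the counseling sessions will be rated for fidelity". D.4.2 has the CM part of CM+CBT sessions recorded on video.

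**The concern.** There are two separate weaknesses. First, occasions that are easy to observe need not have the average duration, and the sign of that selection effect is unknown. Second, observations at the two ends can show that times changed but not when, and the average over the whole study depends on when.

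What is at stake is the incremental cost of mCM. The manual covers CBT time, which both arms use. D.6 cites no manual or standard time for the work that only the mCM arm needs: app training, video review with written feedback, and the CM segment of each session. Video review is not among the staff activities that D.6 names. Yet about ten prompts a week for eight weeks (D.4.2) gives up to 10 x 8 = 80 reviews per mCM participant, or 80 x 70 = 5,600 if half of the 140 are allocated to mCM.

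An error in a unit time applied to every participant stays put when participants are resampled, so a bootstrap of that kind leaves it in place and out of sight. If the primary outcome is not significant, Section F moves to cost minimization, where cost is the whole comparison.

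**Working it through.** The documents give no staff minutes, wages, sample size, window length, window weights or learning rate, so there is no stated figure to reproduce. What follows is an illustration under assumptions.

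**Inputs.** 140 participants treated in sequence (the number to be randomized, D.2). All else is assumed: steady-state time is 1; the initial excess x is 10%, 25%, 50% or 100%; each window holds the first or last 10% or 20% of participants (14 or 28); the two windows get equal weight.

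**Formulas.** Let u run from 0 (first participant) to 1 (last). Time per participant is
- no learning: 1
- linear: 1 + x(1 - u)
- front-loaded: 1 + x * 0.5^(u/h), with half-life h of 10% or 25% of enrolment
- late: 1 + x while u < 0.75, then 1

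With B and E the means of the first and last windows and M the mean over all 140, the error is (B + E)/(2M) - 1. The early-window weight that removes the error is w = (M - E)/(B - E).

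**Two worked cases, x = 50%, windows of 14.**
- Front-loaded, h = 10%: B = 1.3689, E = 1.0007, M = 1.0734. (1.3689 + 1.0007)/2 = 1.1848, and 1.1848/1.0734 - 1 = +10.4%. w = 0.0727/0.3682 = 0.20.
- Late: B = 1.5, E = 1, M = 0.75 x 1.5 + 0.25 x 1 = 1.375. 1.25/1.375 - 1 = -9.1%. w = 0.375/0.5 = 0.75.

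**Error in unit time, % (range over the two window sizes).**

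| Curve | x = 10% | x = 25% | x = 50% | x = 100% |
|---|---|---|---|---|
| None or linear | 0 | 0 | 0 | 0 |
| Front-loaded, h = 10% | +1.3 to +2.2 | +3.1 to +5.4 | +6.1 to +10.4 | +11.4 to +19.4 |
| Front-loaded, h = 25% | +0.9 to +1.3 | +2.0 to +3.2 | +3.8 to +5.8 | +6.6 to +10.2 |
| Late | -2.3 | -5.3 | -9.1 | -14.3 |

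**Can the two windows supply the right weight?** The weight that removes the error is 0.20 to 0.37 for the front-loaded curves, 0.50 for linear and 0.75 for late. The end data cannot choose among these. In the front-loaded case above, the windows show 1.369 and 1.001. A late curve with x = 36.9% shows 1.369 and 1.000, practically the same, but its true mean is 0.75 x 1.369 + 0.25 = 1.277 against 1.073.

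**Where the error goes.** Study therapists treat cases in both arms (D.4.1), so an equal error in CBT time per session drops out of the increment, except for sessions that one arm attends and the other does not. Hypothesis 1a predicts more sessions under mCM, so some of it would remain. Error in mCM-only staff time passes into the increment in full.

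**The case against.** The strongest reply is that the plan already deals with this. The convenience sample supplements other sources, and the end window is there because the authors foresaw a learning curve. With suitable weights the two windows give the right mean under any of the curves tried. The team reports a pilot and long experience with mobile CM monitoring (C.2, D.10), so a large initial excess is speculative. The increment also contains items that do not rest on sampled staff time: expected prizes of about $601 per patient (Table 2; 314 tickets x $1.914 = $601.00), participant time and health care costs. And the plan limits sampling for a stated reason, burden.

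Much of this stands. A reader might infer that staff time comes only from the convenience sample; D.6 says otherwise. A reader might also infer that sampling at both ends must over-weight the learning phase. That needs front-loaded learning and equal weights, and the documents fix neither. A larger error is tempting if each window is shrunk to a single instant. With 30 months of delivery, a 50% excess and a 6-month time constant (the last two assumed), instants give +13.9%, but 3-month windows give +9.1% and 6-month windows +5.6%. Since D.6 samples toward each end, windows are the fair reading.

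What the reply does not answer is that the right weight cannot be learned from the two ends, that selection of occasions is uncontrolled, and that neither shows up in the planned uncertainty analysis.

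**Conclusion.** The concern holds as a risk of bias, not a demonstrated one. The sampled times are non-random and confined to two windows, so unit times may be off in either direction: nil with no or linear learning, about +1% to +19% with front-loaded learning, and about -2% to -14% with late learning. These figures assume equal window weights, windows of 10% to 20% of participants and an initial excess of 10% to 100%. They exclude any effect of choosing convenient occasions, whose sign and size are unknown. They describe the sampled times before any blending with standardized estimates, which could shrink the error by an amount that the plan does not let one calculate.

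The effect on the ICER cannot be computed from the documents. It is likely to be small for CBT time and uncancelled for mCM-specific staff time. Since cost-effectiveness is Aim 2 and the subject of the trial's title, the change is worth making.

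**What to change.** In D.6, replace the convenience sample by a random sample of activities, stratified by activity type and calendar period, with results weighted by the number of activities in each stratum. List video review and feedback as a timed activity. Specifically:
- take session durations from the 10% random fidelity sample (D.8.7), which is at most 0.10 x 140 x 12 = 168 sessions, and CM-segment durations from the CM recordings (D.4.2);
- draw the other activities, and periods that have already passed, at random from the tracking system and counselor records;
- state how sampled times are combined with the standardized estimates.

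Under Aim 2 in Section F, add staff time to the sensitivity analyses, with mCM-specific time varied separately from CBT time.

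The cost is some extra scheduling and record abstraction. Not every activity has to be measured, so the aim of limiting burden is kept. Recordings do not capture preparation time, which would still come from the manual and counselor records.

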Cost and Effectiveness Measurement. Our primary cost effectiveness outcome measure will be the incremental cost-effectiveness ratio (ICER), with costs as the numerator and effectiveness as measured by QALYs as the denominator. Costs will include: intervention delivery costs, participant time costs and health care costs as described above. The QALY is a standardized effectiveness measure, based on the EuroQol (EQ-5D5L), that allows for the comparison of the value of a particular intervention to a broad range of other potential health care investments. Differences in reduction in heavy drinking days and secondary drinking outcomes (e.g., abstinence) among veterans in the mCM+CBT and the CBT comparison group will allow us to identify changes in the QALY effectiveness measure across groups. To estimate the QALYs, we will employ the methods and estimates developed by Barbosa and colleagues (2010), who used a Markov model to assign utility weights to a range of drinking patterns for medical morbidity and mortality, adjusted for health-related quality of life. Incremental costs and effectiveness of mCM+CBT will be compared to those of the CBT comparison group.

D.7. Optional Study Procedure

One of our study therapists, [name], is seeking licensure as a Licensed Professional Counselor, and as part of her supervision, needs to provide video recordings of therapy sessions to her supervisor, [name], MS, LPCS for review. Data will be shared with [name] as view only in a Duke Box folder to which only [name], [name], and [name] have access. Data will be shared in accordance with a data agreement facilitated by Duke’s Office of Research Contracts, and signed by [name] and [name]. This study procedure is fully optional, and is indicated as such during the informed consent process.

D.8. Measures

Participants will complete measures at primary assessment time points (baseline, post-treatment, 6 months post-quit date, and 12 months post-quit date), as well as reporting on alcohol at each CBT session. Follow-ups will be completed in-person.

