Alcohol Readiness to Change	Participant	X		X	X	
Alcohol Purchase Task	Study staff	X		X	X	X
Drinking Norms Rating Form	Participant	X		X	X	X
Alcohol Use, Short Form (PROMIS)	Participant	X		X	X	X
Alcohol Use, Positive Expectancy (PROMIS)	Participant	X		X	X	X
Alcohol Use, Positive Consequences (PROMIS)	Participant	X		X	X	X
Alcohol Use, Negative Expectancy (PROMIS)	Participant	X		X	X	X
Drinking Motives Questionnaire	Participant	X		X	X	X

Alcohol Risk Beliefs	Participant	X		X	X	
Sociodemographic, Clinical, and Process Variables						
Sociodemographic and Military	Participant	X				
DRRI Combat Experiences Scale	Participant	X				
Beck Scale for Suicidal Ideation	Participant	X		X	X	X
Insomnia Severity Index	Participant	X		X	X	X
Dimensions of Anger Reactions	Participant	X		X	X	X
Smoking Exposure Questionnaire	Participant	X		X	X	X
Barratt Impulsivity Scale	Participant	X		X	X	X
Delay Discounting	Participant	X		X	X	X
MOS Social Support	Participant	X		X	X	X
Medical Problems Checklist	Participant	X			X	X
Medications Checklist	Participant	X			X	X
Individual Treatment Alliance	Participant			X		
Working Alliance Inventory	Participant		X*			
Qualitative Interview	Study staff			X		
Satisfaction/Acceptability	Participant			X		
Alcohol Outcome Measures						
Timeline Follow-Back	Study staff	X		X	X	X
Heavy Drinking Days	Study staff	X		X	X	X
% Days Drinking	Study staff	X		X	X	X
Binge Drinking Episodes	Study staff	X		X	X	X
PEth Testing (bioverification)	Study staff				X	X
Addiction Severity Index	Participant	X		X	X	X
Quality of Life, Healthcare Utilization, and Cost Measurement						
EuroQol	Participant	X	X**	X	X	X
Insurance Question	Participant	X				
WHOQOL-BREF	Participant	X		X	X	X
Cost Measurement	Statistical team			X		
Self-Report Healthcare Utilization Measure	Participant	X		X	X	X
Healthcare Utilization	Statistical team	X		X	X	X

* given at CBT sessions 1, 7, and 12 only; ** given at CBT session 7 only

D.8.4. Socio-demographic Measures. Sociodemographic variables will be collected. Social support will be assessed with the MOS social support scale. Impulsivity will be assessed via self-report and through a delay-discounting task (Richards, Zhang, Mitchell, & DeWit, 1999; Garcia-Rodriguez, Secades-Villa, Weidberg, & Yoon, 2013).

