D.8.9. Quality of Life and Health Care Utilization. VA administrative data will be accessed via the VA Corporate Data Warehouse to provide objective measures of VA health care utilization. Our team has extensive experience accessing and utilizing VA data (Elhai, [name], & Ford, 2008; [name], Bosworth, Grambow, Dudley, & [name], 2002; [name], Bosworth, Stechuchak, Strauss, & Butterfield, 2006). Additionally, we will collect self-reported use of non-VA healthcare and 12-step programs and information about insurance coverage. Health care related quality of life will be assessed with the EuroQol (United Kingdom Alcohol Treatment Trial Team, 2005) at baseline and each of the follow-ups.

D.9. Participant Reimbursement

Participants will be paid as follows:

Project Milestone	Amount
Screening visit	\$50
CM abstinence reinforcement	\$611
End-of-treatment visit	\$50
6-month follow-up	\$100
Bioverified abstinence at 6 month follow-up (if randomized to long-term incentive condition)	\$300
12-month follow-up	\$125
TOTAL	\$1236

D.10. Potential Challenges and Solutions

One potential challenge to the success of this project is recruitment and retention. Previous AUD trials in veterans indicate lost-to-follow-up rates near 30% at 12 month follow-up (Hagedorn et al., 2013). We have implemented several methods to increase retention in our trials (e.g., pre-alert letters, birthday cards, reminder

calls, thank you notes) and have obtained excellent retention rates ($>80\%$ at 12-months) in substance using populations (e.g., homeless veterans). We will use these methods and have budgeted to provide an incentive to participants to complete each follow-up. Missing data will be treated as indicative of relapse/heavy drinking. Our pilot data and experience in previous trials indicate that proactive recruitment of veterans with AUD is feasible. To augment our proactive recruitment method, we could include reactive recruitment strategies and include referrals from the SUD clinic at DVHCS. Another potential concern is lost/stolen study equipment. We now have extensive experience with providing veterans with a smartphone and monitoring devices to perform mobile monitoring for CM (e.g., R34AA023877; R01CA196304; 1I01HX001109; 1I01RX001301) and have budgeted for anticipated lost/stolen equipment. Costs of lost equipment will be captured and included in cost analyses.

E. DATA AND SAFETY MONITORING

E.1. Risk/Benefit Ratio

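### The cost-effectiveness analysis is called societal, but its stated health care cost source is VA records and nothing says how the collected non-VA use enters the ICER

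*Combined protocol and SAP*

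**What the plan says.** Section D.6 (Cost Measurement) sets the scope: "Costs to be collected can be grouped into three broad categories: intervention delivery costs, participant time costs, and health care costs". It gives the perspective as the reason for using mean wage rates: "Because we chose to conduct the cost-effectiveness analysis from the societal perspective". The next sentence gives the source of health care costs, which "will be obtained from VA medical records for outpatient, inpatient and medication use". Under Cost and Effectiveness Measurement, the same section defines the ICER numerator: "Costs will include: intervention delivery costs, participant time costs and health care costs as described above".

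Non-VA use is collected. Section D.8.9 says "we will collect self-reported use of non-VA healthcare and 12-step programs and information about insurance coverage". Section D.1 also names both the VA record and participant report as sources of utilization data. Table 3 schedules the "Self-Report Healthcare Utilization Measure" at screening, post-treatment, 6 months and 12 months, in the block headed "Quality of Life, Healthcare Utilization, and Cost Measurement".

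In Section F, Aim 3 counts enrollment in VA and non-VA alcohol treatment. Aim 2 does not mention non-VA care. Its sensitivity analyses vary abstinence, relapse, mortality and the long-term cost of continued drinking.

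**The concern.** A societal perspective counts care whoever pays for it. A numerator whose health care component comes from VA records does not do that, so the result would carry a label that the analysis does not deliver.

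The omitted care is not remote from the trial. Section E.1.4 refers participants to the VA or the university medical center for aftercare, and to a community provider when neither can treat. Alcohol treatment and acute care are services that drinking status could plausibly change. If their non-VA cost differs between CBT plus mCM and CBT alone, the incremental cost is wrong by that difference.

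The exposure does not end if the trial misses its primary outcome. Section F then replaces the ICER with a cost-minimization analysis, in which incremental cost is the whole result.

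**Working it through.** The documents give no ICER, no health care cost and no non-VA cost, so there is no planned figure to reproduce. The check has two parts.

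**1. Tracing non-VA care through the plan**

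- Collected: yes (Sections D.1 and D.8.9, Table 3).
- Given a unit cost: no section does so.
- Included in health care costs: the only source named in Section D.6 is the VA medical record.
- Included in the ICER: the numerator takes its categories from the preceding description, so it inherits the VA source.
- Varied in a sensitivity analysis: not among those listed under Aim 2.
- Used elsewhere: Aim 3, as a utilization outcome rather than a cost.

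Followed as written, the plan produces VA health care cost plus intervention delivery cost plus participant time.

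**2. Illustration of sensitivity**

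Inputs from Section F, Aim 2: utilities of 0.93 (abstinent), 0.82 (at-risk drinking), 0.75 (mild AUD) and 0.67 (severe AUD); thresholds of $50,000 and $100,000 per QALY.

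Assumptions that are not in the documents: a one-year horizon; 10 or 20 percentage points more participants abstinent with mCM; the extra abstainers would otherwise be in a single alternative state; and a $100 per-person difference between arms in omitted non-VA cost.

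Incremental QALY = abstinence difference × (0.93 − utility of the alternative state) × 1 year.

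Shift in ICER = omitted cost difference ÷ incremental QALY.

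| Alternative state | Utility gap | QALY, 10 points | Shift per $100 | QALY, 20 points | Shift per $100 |
|---|---|---|---|---|---|
| At-risk (0.82) | 0.11 | 0.011 | $9,091 | 0.022 | $4,545 |
| Mild AUD (0.75) | 0.18 | 0.018 | $5,556 | 0.036 | $2,778 |
| Severe AUD (0.67) | 0.26 | 0.026 | $3,846 | 0.052 | $1,923 |

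The range is therefore about $1,900 to $9,100 per QALY for each $100. The shift is proportional to the cost difference: at 10 points against mild AUD, $500 ÷ 0.018 = $27,778. A smaller effect enlarges it: at 5 points against at-risk drinking, $100 ÷ 0.0055 = $18,182. The sign follows the sign of the cost difference, which could go either way.

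**The case against.** The strongest reply is that this is an unwritten step rather than a decision to leave non-VA care out. Section D.6 never says that VA records are the only source, participant report is a named source of utilization data, and Table 3 puts the self-report measure in a block whose heading includes cost measurement. That makes an intention to cost these data plausible. It does not settle the matter: a heading is not a costing rule, and the one sentence that does name a cost source names the VA record directly after the societal perspective is declared.

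A second reply is that non-VA use may be small or balanced. Participants must be enrolled in VA primary care, those in professional behavioral treatment for AUD are excluded, participants are asked not to start new AUD treatment during the treatment period, and referrals go to the VA first. Equal non-VA cost in both arms cancels in the increment. This stands as a limit on what can be claimed. It does not make the difference zero, since referral outside the VA is provided for and follow-up runs well beyond the treatment period.

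A third reply concerns size. Section F frames Aim 2 over the lifetime, although it also bases QALY change on drinking status from baseline to 12 months. If effects persist, a lifetime horizon gives a larger QALY gain, and a given cost difference moves the ICER less. That also stands.

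Finally, adding non-VA care would not make the analysis societal. The three cost categories would still leave out costs of drinking that fall outside health care and participant time. This is correct, and it means that the label has to change as well as the cost base.

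**Conclusion.** The stated perspective and the stated cost source do not match, and no other part of the plan reconciles them. As written, Aim 2 leaves non-VA care out of the ICER or the cost-minimization result.

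A reader might infer that the ICER will be biased, or biased in favor of mCM. The documents do not support that. Bias needs a between-arm difference in non-VA cost, on which they give no data, so both direction and amount are unknown. Nor are the dollar figures above estimates. They rest on an assumed abstinence difference, an assumed cost difference, a one-year horizon and a choice of alternative drinking state. They show only that, with a QALY gain of a few hundredths or less, modest omitted cost differences are not negligible against the plan's thresholds.

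The point concerns Aim 2. It does not touch the primary endpoint, heavy drinking days at 6 months.

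**What to change.** Preferred: state in Section D.6 and under Aim 2 that self-reported non-VA visits, admissions and alcohol treatment will be valued with a named set of national unit costs and added to VA costs in the primary ICER (and in the cost-minimization analysis, if that applies). Report a VA-only version as a sensitivity analysis. Describe the perspective as health-care sector (all payers) plus participant time.

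Alternative: if non-VA care will not be costed, restate the perspective as VA payer plus participant time.

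Whichever is chosen should be fixed before costs are compared between arms, so that the cost base cannot be selected on the result. The preferred change needs no new data collection. It takes some analyst time and accepts recall error in self-reported use, which the VA-only analysis helps to put in context. The alternative is a one-line edit.
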